## **Background**

Drunk driving is a major public health problem. The National Highway Traffic Safety Administration reported nearly 10,000 people died from alcohol-related crashes in the U.S. in 2014 (National Center for Statistics and Analysis, 2015). This translates into over 1 DUI related death per hour every day of the year. The problem is further magnified when one considers that each year over 1.3 million drivers in the U.S. are arrested for driving under the influence (DUI) (Department of Justice, 2013). This results in over 3.5 thousand DUI arrests per day. As alarming as these statistics are they pale by comparison to estimates indicating that they only represent 1 percent of the 121 million self-reported episodes of alcohol-impaired driving among U.S. drivers each year (Jewett et al., 2015). Drunk driving also does not only affect the driver. Almost 1 in 5 of all alcohol-related driving fatalities are passengers (NHTSA, 2011). Finally, youth under 21 are significantly over-represented in both alcohol-related driving and alcohol-related passenger fatalities relative to the proportion of all licensed drivers (NHTSA, 2014; Shults et al., 2009; Chen et al., 2008). Together these statistics all underscore the need for immediate action to curb these alarming trends.

There has been a wealth of research dedicated to identifying factors that influence DUI, riding with drinking drivers (RWDD), and under-age drinking to curb these alarming trends. Policies and regulatory actions that focus on maintaining the drinking age at 21, graduated licensing, sobriety check points, server training, and zero tolerance have all been shown to effectively reduce underage drinking and DUI (Hingson et al., 1994; Voas et al., 2000; Hingson et al., 2004; Shults et al., 2001). Despite these efforts, youth continue to engage in DUI, RWDD, and abuse alcohol before they are 21. This indicates a great need to effect change on their motivations and risky behavior through efficacious prevention efforts.

The research proposes to move the field forward by conducting a randomized controlled trial of MADD's parent-based intervention's (PBI) efficacy for all three categories of risky behavioral tendencies (underage drinking, DUI, and RWDD) on a nationally representative sample assessed at 3-waves (baseline, 6 mo., and 12 mo). To the extent that the research is successful, it will provide an easy to implement and low cost alternative that can be widely disseminated to address this important public health problem.

## **Objectives**

Three objectives for the research: 1) Evaluate the efficacy of the PBI (short and long term); 2) examine the mediators of the PBI that directly influence drinking, DUI, and RWDD behaviors; and 3) identify the moderators of intervention efficacy (the subgroups for whom the intervention is more vs less effective).

## **Study Design**

A randomized 3-arm intervention (PBI, Surgeon General, Active Control) with 3 waves of online survey data collection for parents (baseline, 6-month, 12-month), and 4 waves for teens (baseline, 1-month, 6-month, 12-month).

## **Recruitment Strategy**

The participants were recruited by Ipsos using their proprietary KnowledgePanel. Parent-teen dyads who met inclusion criteria were invited to participate in the study via email. Up to 7 email reminders were sent to participants who did not complete the survey initially.

## **Study Population**

The eligibility *inclusion criteria included*: Parent – must have a teenager aged 15-18 years old; Teen – must be 15-18 years old and have a parent/guardian agree to participate in the study. *The exclusion criteria were*: Parent – did not have a teenager aged 15-18; Teen – was not 15-18 years old or did not have a parent/guardian agree to participate in the study.

Participants were required to provide online consent to participate. Parent participants received a description of the research and Ipsos' contact information for questions or to decline participation. Parents were presented a screen describing the research, their consent form, as well as a parental assent statement. Once parents provide consent, they were routed to the baseline survey; after parents provide assent for their teen, teens were also provided with an assent form, and then were routed to their baseline survey.

### **Sample Size, Power, and Attrition**

*Sample Size/Statistical Power*: The sample sizes were chosen based on statistical analytic and theoretical considerations. For example, for Aim 1 examining efficacy of the PBI, we aimed to have final dyad sample Ns of 588 and 532 (and approximately equal n's for our PBIs and control groups of 294 and 266) at the 6 and 12 month follow-ups, respectively. Using power estimation procedures described in Cohen (Cohen & Cohen, 1983) these sample sizes will yield power of greater than 0.80 for small effect sizes (e.g., 5-10%) in the MANCOVA-based analyses (omnibus tests, interactions, and planned comparisons). In our published papers with similar Ns comparing drinking for PBI and controls ([name] et al., 2013; Doumas et al., 2013; Ichiyama et al., 2009; [name] et al., 2009; Testa et al., 2010; [name] et al., 2001; [name] et al., 2004) we have detected effect sizes of .05 to .09 for main effects and .05 to .08 for interactions. Thus, with our final Ns we should have sufficient power to evaluate Aim 1.

*Attrition*: We will first examine if the attrition is random by forming a dummy variable that indicates completion or drop-out at each assessment. The dummy variable will be correlated with key variables in the study (e.g., Group, drinking/DUI/RWDD outcomes). In the past, we have observed nonsignificant correlations suggesting that the attrition has been random and then used the most advanced multiple imputation techniques to impute missing data. We then analyze all cases with the imputed data ([name] et al., 2009). Although we have not observed differential attrition by condition in our previous work, we recognize the potential. We will reduce this possibility by providing the controls with an online link to the intervention at the completion of the 12-month assessment. Thus, all conditions will be identical except for the timing of intervention. However, if we should observe non-trivial correlations (e.g., > .2) between the dummy variable reflecting completers vs. drop-outs, we will include the dummy coded variable as a covariate in subsequent analyses and attempt to interpret significant effects.

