### **Measures**

Data were collected online at baseline, 6-month, and 12-month for both parents and teens. Teens also had a 1-month follow-up. Ipsos provided demographic information on the parents based on panel demographics. Other measures included: DUI, riding with drinking drivers; alcohol use; intentions/willingness/attitudes/beliefs/norms to drink/DUI/RWDD; parental monitoring, permissiveness, modeling; intervention fidelity (Chen et al., 2008; Hultgren et al., 2015; Kann et al., 2014; Poulin et al., 2007; Abar et al., 2014; Mallett et al., 2011; Cartwright & Asbridge, 2011; Dhami et al., 2011; Collins et al., 1985; Dimeff et al., 1999; Marlatt et al., 1998; [name] & Jaccard, 1992; Grube & Voas, 1996; Beck & Treiman, 1996; Abar et al., 2009).

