### **Primary Outcome Measure**

The primary outcome measures were typical weekend drinking, and declining to ride with impaired drivers.

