### **Statistical Analysis Plan**

Statistical analyses were performed using IBM SPSS Statistics version 28. Each primary and secondary outcome was examined using Tukey's critical difference value to compare the means following Wilkinson et al., (1999) recommendations. This approach has been shown to have the most power and least Type I error rates with varying sample sizes to compare mean differences between conditions.

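### The sample size is justified by power in MANCOVA, but the analysis plan states only an unadjusted Tukey comparison of means; the two are unreconciled and the baseline values go unused

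*Combined protocol and SAP*

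**What the plan says.** Under Sample Size, Power, and Attrition, the power claim for Aim 1 is made "in the MANCOVA-based analyses (omnibus tests, interactions, and planned comparisons". The covariates are not named. A separate paragraph in that section, on attrition, gives a conditional rule: if completion status shows non-trivial correlations with key study variables (the example threshold is .2), "we will include the dummy coded variable as a covariate in subsequent analyses".

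The Statistical Analysis Plan names the software and one method: "Each primary and secondary outcome was examined using Tukey's critical difference value to compare the means". It justifies this choice by power and Type I error "with varying sample sizes to compare mean differences between conditions". It mentions no MANCOVA, adjusted means, covariate, omnibus test or interaction.

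Three other statements matter here. The design is "A randomized 3-arm intervention (PBI, Surgeon General, Active Control", with one further survey for teens at 1 month. Two outcomes are primary: "The primary outcome measures were typical weekend drinking, and declining to ride with impaired drivers". The Measures section says "Data were collected online at baseline, 6-month, and 12-month for both parents and teens", and its list covers alcohol use, riding with drinking drivers and willingness.

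**The concern.** The analysis that justifies the sample size is not the analysis the plan states. The first is multivariate and covariate-adjusted. The second takes one outcome at a time and, as written, uses raw means. The sample-size section is written in the future tense and the analysis plan in the past tense, so the method may have changed in between, but the document does not say so.

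Two things are at stake:

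- **Precision.** If the raw means are compared, the baseline value of each outcome is left out, although it is usually the strongest available predictor of the follow-up value.
- **Prespecification.** If the adjusted and unadjusted results differ, the document does not settle which one was planned. The conditional dropout covariate has no stated model to enter.

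**Working it through.** **Inputs from the documents.** Three arms; target totals of 588 dyads at 6 months and 532 at 12 months; 294 and 266 per group; an effect of 5-10%; power above 0.80.

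**Assumptions, because the documents give no figure.** Two-sided alpha 0.05; the effect read as proportion of variance explained; equal arms; normal outcomes; correlation r between baseline and follow-up of 0.3, 0.5 or 0.7.

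**Step 1: the plan's own figure.** F-test power uses f² = R²/(1 − R²) and noncentrality f² × N. For R² = 0.05, f² = 0.05/0.95 = 0.0526, so the noncentrality is 30.9 at N = 588 and 28.0 at N = 532.

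| Numerator df | Power, N = 588 | Power, N = 532 |
|---|---|---|
| 1 | 0.9998 | 0.9996 |
| 2 | 0.9994 | 0.9985 |
| 6 | 0.9946 | 0.9891 |

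The claim of more than 0.80 reproduces on this reading. It would not if 0.05-0.10 were Cohen's f: with 1 df, power is 0.23-0.68 at 588 and 0.21-0.63 at 532. The metric is not stated.

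**Step 2: the same effect under Tukey.** For two equal groups, R² = 0.05 corresponds to d = 2 × √(0.05/0.95) = 0.459. The critical value is the 0.95 quantile of the studentized range for three means divided by √2, about 2.35. The noncentrality is d × √(n/2).

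- With 294 or 266 per arm, power is 0.999 or 0.998.
- With the totals split over three arms (588/3 = 196; 532/3 ≈ 177), power is 0.986 or 0.975.

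The change of method does not endanger power at the stated effect.

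**Step 3: what the unadjusted comparison gives up.** Adjusting for a baseline value with correlation r multiplies the residual standard deviation by √(1 − r²), so the noncentrality becomes d × √(n/2)/√(1 − r²), at the cost of one residual degree of freedom. The factor is 0.954, 0.866 or 0.714, so the detectable difference shrinks by 5%, 13% or 29%. The d detectable with 80% power is:

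| n per arm | Unadjusted | r = 0.3 | r = 0.5 | r = 0.7 |
|---|---|---|---|---|
| 294 (6 months) | 0.263 | 0.251 | 0.228 | 0.188 |
| 266 (12 months) | 0.277 | 0.264 | 0.240 | 0.198 |
| 196 (588 over three arms) | 0.323 | 0.308 | 0.279 | 0.230 |

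At the difference where the unadjusted comparison has power 0.80, the adjusted comparison has 0.84, 0.91 or 0.98.

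Both sets of n are shown because 588 = 2 × 294 and 532 = 2 × 266. The stated totals therefore fit two groups of that size, not three. The percentage gain is the same on either reading.

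**The case against.** The strongest reply is that there is no contradiction. The sample-size section is a rationale given by example; the Statistical Analysis Plan expressly covers every primary and secondary outcome and so governs. Its silence on covariates does not exclude them, and Tukey's procedure is routinely run on adjusted means. This stands in part: the two sections are compatible in principle. But the plan speaks only of comparing means, and a reader would have to supply both the adjustment and the covariate list. The sample-size section does not name baseline as a covariate either, so the model proposed below is a recommendation and not a reconstruction of what was intended.

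Several stronger readings are tempting, and the documents do not support them:

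- **That the two sections cannot both be followed.** They can, with Tukey on adjusted means, including when the dropout rule is triggered.
- **That the dropout dummy belongs to the powered MANCOVA.** It comes from the attrition paragraph and applies only if correlations are non-trivial.
- **That Tukey on each outcome doubles the false-positive rate.** Two independent outcomes give 1 − 0.95² = 9.75%, against 5% for one omnibus test. But the sample-size section also lists planned comparisons and does not make them conditional on the omnibus test. One such 5% contrast per outcome gives the same 9.75%.
- **That adjusted and unadjusted verdicts would often differ.** In simulation they differ in 7-19% of trials, but only at d = 0.263-0.277, which is 1.7-1.9% of pairwise variance by d²/(d² + 4), and with 294 or 266 in each of three arms. At 5% of variance they differ in under 0.2%.
- **That the powered interactions are the moderator tests.** The power statement is tied to Aim 1. Objective 3, to "identify the moderators of intervention efficacy (the subgroups for whom the intervention is more vs less effective", has no stated analysis, but that is a separate omission.

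**Conclusion.** The point holds as a failure to reconcile two sections, with an avoidable loss of precision. The sample size rests on covariate-adjusted multivariate analyses; the only stated analysis is a per-outcome Tukey comparison that, as written, adjusts for nothing and gives the conditional dropout covariate no place.

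The cost is a detectable difference that is larger than it need be: adjustment would reduce it by 5%, 13% or 29% at r = 0.3, 0.5 or 0.7. These correlations and alpha are assumptions. The gain depends on r and would be small if baseline predicts follow-up weakly.

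A reader might infer that the trial is underpowered. It is not at 5% of pairwise variance, where power exceeds 0.97 with or without adjustment. The loss matters for smaller effects and for knowing which result was planned.

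**What to change.** In the Statistical Analysis Plan, name one primary analysis, for example: each primary and secondary outcome at each follow-up is analysed with a linear model containing arm (three levels) and the baseline value of that outcome; adjusted means are compared pairwise with Tukey adjustment at a stated familywise alpha; the unadjusted Tukey comparison is a sensitivity analysis. Measures are listed by domain only, so confirm that each outcome item was asked at baseline in the same form.

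Align the sample-size section with that analysis: say whether a MANCOVA is still intended, and give alpha, the metric of the 5-10% effect, and whether 294 and 266 are per arm. If the dropout rule is kept, apply it in this model on the imputed data, since the dummy is constant among completers.

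If results already exist, report both analyses and say which was prespecified.

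The cost is low: the baseline surveys are in hand and a few models are re-run. The downside is that adjusted results may differ from those already obtained. This change does not address multiplicity across the two primary outcomes and does not supply the moderator analysis.

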### **Sample Characteristics**

Of those invited, 1,176 (28.5%) met the study eligibility criteria of being a parent or legal guardian to a 15-18 year old adolescent-teen and consented for both themselves and their teen to participate in the study. There were 562 (13.6%) participants who responded to the study invitation but did not meet the study eligibility criteria. Eligible dyads were randomly assigned to one of three conditions: Active Control (AC; n=390, 33.1%), Surgeon General (SG; n=393, 33.4%), or Mothers Against Drunk Drinking Parent-Based Intervention (MADD PBI; n=393, 33.4%).

At the T1 baseline survey, the average age of the teens was 16.33 (SD=1.09). About half of teens identified as female (49%) and most parents identified as female (54%). The majority of participants identified as White (78.2%), Black (8.7%), Asian (2.9%), Native Hawaiian or Pacific Islander (0.2%), American Indian or Alaska Native (1.2%), Multiracial (4.1%), Other (4%), and Hispanic (26.9%).

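### Adding the dropout indicator as a covariate does not correct attrition bias, and in imputed data without baseline adjustment it can bias the arm comparison

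*Combined protocol and SAP*

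**What the plan says.** Under Sample Size, Power, and Attrition, the plan codes completion or dropout at each assessment. It then states: "The dummy variable will be correlated with key variables in the study (e.g., Group, drinking/DUI/RWDD outcomes"). The history offered is that "In the past, we have observed nonsignificant correlations suggesting that the attrition has been random", after which the team imputed and analysed every case. The contingency opens "if we should observe non-trivial correlations (e.g., > .2") and the action is "we will include the dummy coded variable as a covariate in subsequent analyses and attempt to interpret significant effects". No other analysis step is given for that situation. Offering controls the intervention link after 12 months is a retention measure.

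The analysis model is described in two places. The sample-size text claims power "in the MANCOVA-based analyses (omnibus tests, interactions, and planned comparisons") without naming covariates. The Statistical Analysis Plan section says "Each primary and secondary outcome was examined using Tukey's critical difference value to compare the means", and names neither a covariate nor a missing-data method. Baseline values exist, because under Measures "Data were collected online at baseline, 6-month, and 12-month for both parents and teens".

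**The concern.** Randomisation makes the arms comparable as a whole. It does not make them comparable within completers or within dropouts, because dropout happens afterwards and may depend on arm. If heavier drinkers leave more often, and more people leave one arm than the other, then the remaining participants differ between arms at baseline, and so do those who left. A model containing the dropout indicator averages these two non-comparable contrasts.

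The rule is meant to apply exactly when dropout appears to be related to arm or outcome, which is when this matters. Depending on which arm loses more, a real benefit can be hidden or exaggerated. The plan also does not say whether imputation continues once the trigger is met, so both readings have to be checked.

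**Working it through.** **The plan's own figures.** The plan gives no figure for attrition bias. The only checkable claim in the section is power above 0.80 with 294 and 266 per group. Taking 5% as variance explained, f² = 0.05/0.95 = 0.053. A two-group F test at an assumed two-sided 5% then gives 0.9998 and 0.9996, so the claim reproduces on that reading. It has no bearing on bias.

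**Expected loss (inferred; the plan does not state it).** Randomised: 390 + 393 + 393 = 1,176, about 392 per arm. Per group: 1 - 294/392 = 25% at 6 months and 1 - 266/392 = 32% at 12 months. If the planned totals of 588 and 532 were meant for all three arms, loss would be 1 - 588/1,176 = 50% and 1 - 532/1,176 = 55%.

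**Assumed model (not from the documents).** Y = 0.6·X + noise + effect·arm, where X is the baseline outcome and both have SD 1. Dropout: logit P(D=1) = c(arm) + 1·X, with 34% loss in controls and 16% in an intervention arm. The imputation model contains arm and X. Positive bias means the intervention looks worse.

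**Reading 1, completers only.** The same-wave indicator is constant and drops out of the model. Integrating over X, mean baseline among those who stay is -0.284 (control) and -0.141 (intervention). Bias = 0.6 × (-0.141 + 0.284) = 0.086 SD, with or without the indicator. An indicator from a later wave does vary among 6-month completers. With further loss of 12% and 7% by 12 months, adding it moved the bias from 0.087 to 0.110.

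**Reading 2, imputed data plus indicator.** The arm coefficient is a weighted mean of the two within-stratum contrasts.
- Stayers: 0.086, as above.
- Dropouts: mean baseline 0.552 (control) and 0.739 (intervention), so 0.6 × 0.187 = 0.112.
- Weights for equal arms: stayers 0.66 × 0.84/(0.66 + 0.84) = 0.370; dropouts 0.34 × 0.16/(0.34 + 0.16) = 0.109. The stayers' share is 0.370/0.479 = 0.77.
- Bias = 0.77 × 0.086 + 0.23 × 0.112 = 0.092 SD. With the arms swapped it is -0.092.

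**Simulated error rates, no true effect.** Three arms of 392, dropout 34/25/16%, comparing the outer arms; 20 imputations pooled by Rubin's rules; Tukey critical t 2.347, nominal 1.9% per comparison.

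| Analysis | Bias (SD) | False positives |
|---|---|---|
| Completers, unadjusted | 0.09 | 9.8% |
| Completers + baseline | 0.00 | 1.9% |
| Imputed | 0.00 | 1.8% |
| Imputed + indicator | 0.09 | 10.6% |
| Imputed + baseline | 0.00 | 2.2% |

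With dropout 34/16/16%, the indicator gives 11.8% and 10.5% for the two comparisons with control.

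**True effect -0.20 SD.**

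| Analysis | Estimate | Tukey power |
|---|---|---|
| Imputed | -0.20 | 55% |
| Imputed + indicator, controls lose more | -0.11 | 17% |
| Imputed + indicator, intervention loses more | -0.29 | 91% |
| Imputed + baseline | -0.20 | 71-72% |

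**Varying the inputs (imputed + indicator, no true effect).**
- Log-odds 0.5, 34% against 16%: 0.05 SD, 4.1% false positives.
- Log-odds 1, 30% against 20%: 0.05 SD, 4.1%.
- Log-odds 0.5 and 30% against 20% together: 0.03, 0.02 and 0.01 SD at baseline-outcome correlations 0.6, 0.4 and 0.3.
- Equal 25% loss, or dropout unrelated to baseline: no bias.
- Baseline outcome also in the analysis model: 0.00 SD.
- Dropout driven by the unobserved outcome (log-odds 1): imputed 0.10, plus indicator 0.15, imputed + baseline 0.10 SD.

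**The case against.** The harm from the indicator needs a combination that the plan does not spell out: imputed data, baseline in the imputation model, baseline absent from the analysis model, and dropout related to both arm and prognosis. Each link can be questioned.

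- **Imputation model.** None is specified. If baseline is left out of it, the bias is 0.087 SD without the indicator and about the same with it. This stands as a condition on the harm. The bias is still uncorrected.
- **Baseline adjustment.** A MANCOVA has covariates, and baseline may have been one of them. If so, the indicator adds no bias. The text leaves this open, and in that case baseline does the correcting.
- **Trigger.** The sentence does not name the second variable in the correlation, and it follows a remark on differential attrition by condition. If it means arm only, r = .2 with two equal arms needs a gap of 0.4 × √(q(1-q)), which is 17 points at 25% loss and 19 at 32%. The 30% against 20% case (r = .115 with arm) would then not trigger it. If outcomes count, as the earlier list in the same paragraph suggests, a correlation of about .36 with baseline would.
- **Size.** All inputs are assumed, including a normal outcome, and weaker combinations give very little bias.
- **Use.** The Statistical Analysis Plan section is in the past tense and mentions no indicator, so nothing shows that the rule was ever applied.

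A dropout indicator is legitimate in a pattern-mixture model with arm-by-pattern terms averaged over patterns. The plan describes only a covariate.

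These points limit when the rule does harm. None identifies a situation in which it reliably corrects attrition bias.

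**Conclusion.** The concern holds. On either reading of the paragraph, the stated response to non-random attrition leaves the bias in place. In imputed data it can restore a bias that imputation had removed: about 0.09 SD and roughly 11% false positives per comparison under the stronger assumed inputs, falling to 0.01 to 0.03 SD under the weakest combination tried. The direction follows whichever arm loses more. The mechanism is certain; its size in this trial cannot be known from the documents. When dropout depends on measured baseline, having the baseline outcome in the analysis model removes the bias, with imputed or completer data. When it depends on the unobserved outcome, neither imputation, baseline adjustment nor the indicator removes it, and in the case run the indicator made it worse.

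**What to change.** 1. Delete the indicator-as-covariate rule and its correlation trigger.
2. State that all randomised dyads are analysed whatever the dropout correlations show, by multiple imputation with arm, baseline outcomes, demographics and earlier waves as predictors, or by an equivalent likelihood model.
3. Name the baseline value of each outcome as a covariate in the analysis model, so that the MANCOVA wording and the Statistical Analysis Plan section agree.
4. Report dropout by arm and wave.
5. Optionally, add a delta or tipping-point sensitivity analysis for dropout that depends on the unobserved outcome.

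The cost is SAP wording and a modest reanalysis; no new data are needed. As parts of the document already report completed work, any change made after data collection should be labelled post hoc.
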